1.1. SYNOPSIS

Name of Sponsor:	Fondazione Gabriele d'Annunzio - Chieti	
Name of Finished Product:	Lixiana	
Name of Active Substance:	Edoxaban	
Title of the Study:	A pilot study on Edoxaban for the resolution of left atrial thrombosis in patients with non-valvular atrial fibrillation	
Abbreviated Title:	Edoxaban in AF	
Study Coordinating Investigator:	[name] [name]	
Study Centres:	A total of 6-8 Italian sites will be involved.	
Background	Current guidelines indicate a ≥3 weeks therapy with VKAs to allow the resolution of LA or LAA thrombus in patients with atrial fibrillation before cardioversion.	
Rationale:	
Isolated reports have indicated that complete LA or LAA thrombus resolution may be achieved also with use of oral Factor Xa inhibitors, which have demonstrated the same efficacy but a better safety profile compared to warfarin.
 
The aim of this open-label pilot study is to investigate the percentage of LA/LAA thrombus resolution with edoxaban therapy in patients with non-valvular atrial fibrillation. The subordinated aim is the design a larger and longer study to compare edoxaban and warfarin in the same patient population.
	
Planned Study Period:	Start of enrolment: November 2017 End of enrolment: February 2019	Clinical Phase: Phase 2
Objectives:	
The primary objective of the study will be the definition of the percentage of patients who, after 4 weeks of edoxaban treatment, will experience complete thrombus resolution by TEE.
 
Secondary objectives will be the assessment of bleeding events after 4 weeks of treatment with edoxaban and, after the same period, the incidence of any stroke or peripheral embolism and the time, when applicable, to electrical cardio-version.
	
Methodology:	Non-controlled, open-label, 4 weeks pilot study.	
Number of patients:	A total of 25 patients will be included in the study.	
Diagnosis and Criteria for Inclusion:	
Inclusion criteria
 
Patients with all the following criteria will be eligible for inclusion in the study protocol:
 
 1. Signed written informed consent. 2. Males and females ≥ 18 years of age. 3. Female subjects must be post-menopausal (for at least 2 years), surgically sterile, abstinent, or, if sexually active, be practicing an effective method of birth control (e.g., prescription oral contraceptives, contraceptive injections, intrauterine device, double-barrier method, contraceptive patch, male partner sterilization) before entry and throughout the study; and, for those of 	

	
childbearing potential, have a negative serum β-hCG pregnancy test at screening.
 
4. Atrial fibrillation (AF) must be documented by ECG evidence (e.g., 12-lead ECG, rhythm strip, Holter, pacemaker interrogation) within 30 days before enrolment.
 
5. Subjects with newly diagnosed atrial fibrillation are eligible provided that:
 
• -there is evidence that the atrial fibrillation is non-valvular;• -there is ECG evidence on 2 occasions 24 hours apart demonstrating atrial fibrillation. 
6. LA or LAA thrombosis documented by trans-esophageal echocardiography (TEE)
 
7. CHA₂DS₂-VAS_C score >1.


Exclusion criteria
 
Patients with all the following criteria will not be eligible for inclusion in the study protocol:
 
1. Hemodynamically significant mitral valve stenosis.2. Prosthetic heart mechanical or biological valve (annuloplasty with or without prosthetic ring, commissurotomy and/or valvuloplasty are permitted).3. Transient atrial fibrillation caused by a reversible disorder (e.g., thyrotoxicosis, pulmonary embolism, recent surgery or myocardial infarction).4. Known presence of atrial myxoma.5. Left ventricular thrombus.6. Active endocarditis.7. Active internal bleeding.8. History of condition associated with increased bleeding risk including, but not limited to:
• major surgical procedure or trauma within 30 days;• clinically significant gastrointestinal bleeding within 6 months;• previous intracranial, intraocular, spinal, atraumatic intra-articular bleeding;• chronic haemorrhagic disorder;• Any neoplasm, including intracranial neoplasm,• arteriovenous malformation or aneurysm.9. Platelet count <90,000/μL at the screening visit.10. Sustained uncontrolled hypertension: SBP \geq180 mmHg or DBP \geq100 mmHg.11. Severe, disabling stroke (modified Rankin score of 4 to 5, inclusive within 3 months or any stroke < 14 days).12. Transient ischemic attack within 3 days.13. Any oral anticoagulant therapy at the time of the baseline visit.14. Treatment with:
• aspirin >160 mg daily;• aspirin plus a thienopyridine within 5 days;• intravenous antiplatelets within 5 days;• fibrinolytics within 10 days.15. Anticipated need for therapy with a non-steroidal anti-inflammatory drug in the next 4 weeks.16. Treatment with a strong inducer of cytochrome P450 and P glycoprotein, such as ketoconazole, itraconazole, voriconazole, posaconazole, ritonavir, lopinavir,	

	
telaprevir, indinavir, conivaptan, claritromycin or planned treatment during the study.
 
 17. Other indication for anticoagulant therapy. 18. Hypersensitivity or intolerance to the study drug, including excipients. 19. Women of childbearing potential who do not want adopt a contraceptive method during the study period and the following 4 weeks. 20. Breast-feeding women during the study period and the following 4 weeks. 21. Anemia (hemoglobin <10 g/dL) at the screening visit. 22. Known significant liver disease (e.g., acute clinical hepatitis, chronic active hepatitis, cirrhosis), or ALT or AST >2 x ULN or total bilirubin >1.5 x ULN. 23. Patients with moderate or severe renal impairment (CrCL <50 mL/min) or patients with end stage renal disease (CrCL < 15 mL/min) or on dialysis.
Test Product, dose and duration of treatment	All patients will receive edoxaban 60 mg once a day, with open-label design, for 4 weeks. Edoxaban daily dose will be reduced to 30 mg/day in case of: body weight ≤60 kg, or concomitant therapy with verapamil/quinidine/dronedarone.
Statistical Methods:	
Sample Size There are no previous studies conducted with edoxaban on atrial thrombus dissolution and this is a pilot trial. For this reason sample size has been determined empirically, on the basis of case reports with similar products in this clinical conditions (6, 8-10, 15). However, if the proportion of patients with thrombus dissolution after 4 weeks of treatment will be 60%, which is compatible with the above mentioned case reports, a sample size of 25 produces a two-sided 95% confidence interval with range 39-79%.
 
Primary Analysis Primary outcome will be the detection of the percentage of patients, after 4 weeks of edoxaban treatment, with complete thrombus resolution by TEE, evaluated with the following Probe angulations: 0°, 45°-to-60°, 90°. As this is a single arm, open-label study, in principle, only a descriptive statistical analysis will be performed for the primary criterion.
 
Secondary analyses Secondary endpoints will be: absolute and percent variation of thrombus area at 4 weeks by TEE evaluation (Probe angulations: 0°, 45-to-60°, 90°) and time to electrical cardio-version (when applicable). Only a descriptive statistical analysis will be performed for the secondary criterion.
 
Safety analysis Analyses of the safety criteria that will include: percentage of bleeding events at 4 weeks and after 8 weeks (telephone assessment) after the end of the treatment; percentage of any stroke or peripheral embolism at 4 weeks and after 8 weeks (telephone assessment) after the end of the treatment; percentage of any other safety related events (deaths, SAEs and AEs).

Study flow-chart

Timing	BASELINE	FOLLOW-UP	PHONE ASSESSMENT
	Day 0	Week 4 (± 3 days)	Week 8 (± 3 days)
Confirmation of consent	■		
Verification of inclusion/exclusion criteria	■		
Demographic data	■		
Medical history	■		
CHA ₂ DS ₂ -VAS _C score and HAS-BLED score	■		
Information regarding AF	■	■	
Blood pressure, heart rate	■	■	
EKG	■	■	
Transthoracic echocardiogram	■	■	
Transesophageal echocardiogram	■	■	
Blood count; liver and renal function	■	■	
Concomitant treatments	■	■	
Bleeding events		■	■
Thromboembolic events		■	■
Other adverse events		■	■
Study drug dispensation	■		
Compliance		■	
Study completion form			■

1.2. LIST OF ABBREVIATIONS

ADR	: Adverse Drug Reaction
AE	: Adverse Event
AF	: Atrial Fibrillation
ALT	: Alanine aminotransferase
AST	: Aspartate aminotransferase
ATC	: Anatomical Therapeutic Chemical Classification System
CHA ₂ DS ₂	: Cardiac failure, Hypertension, Age (x2), Diabetes, Stroke (x 2) risk index
CI	: Confidence Interval
CRA	: Clinical Research Associate
CRF	: Case Report Form
DBP	: Diastolic Blood Pressure
EC	: Ethic Committee
ECG	: Electrocardiogram
FAS	: Full Analysis Set
GCP	: Good Clinical Practice
HR	: Hazard Ratio
ICH	: International Conference on Harmonisation
LA	: Left Atrial
LAA	: Left Atrial Appendage
MedDRA	: Medical Dictionary for Regulatory Activities
NOAC	: Non vitamin K oral anticoagulants
OAC	: Oral Anticoagulant Therapy
PP	: Per Protocol
SAE	: Serious Adverse Event
SBP	: Systolic Blood Pressure
SEE	: Systemic Embolic Events
SmPC	: Summary of Product Characteristics
TEE	: Trans Esophageal Echocardiography
ULN	: Upper Level of Normal
VKA	: vitamin K antagonists
WHO	: World Health Organization

2. INTRODUCTION AND STUDY RATIONALE

2.1. TARGET PATHOLOGY AND THERAPY

It is estimated that atrial fibrillation (AF) affects up to 2% of the general Western World population, and up to 5% of acute stroke patients. The lifetime risk of developing an episode of AF is up to 25% in those who have reached the age of 40 (1).

AF is associated with increased rates of death, stroke and other thromboembolic events. Death rates are doubled by AF, whereas stroke is often severe and results in long-term disability. It is estimated that about 20% of stroke is due to AF (1). Moreover, hospitalizations due to thromboembolic complications and progressive cognitive dysfunction due to asymptomatic embolic events are also ascribed to AF (1).

Current guidelines indicate a ≥3 weeks therapy with vitamin K antagonists (VKAs) to allow the resolution of left atrial (LA) or left atrial appendage (LAA) thrombus in patients with atrial fibrillation (1) before cardioversion.

The presence of LA and LAA thrombi is usually detected by transesophageal echocardiography (TEE). When thrombus is detected, the percentages of thrombus resolution with VKAs vary, in various studies, from 55% to 85% usually in 4 weeks time (2-5). Such range is at least in part related to the level of anticoagulant activity obtained, and resolution likely depends on optimal anticoagulation intensity under VKA treatment, which is sub-optimal in the induction phase of VKA treatment.

Isolated reports (6, 15) have indicated that complete LA or LAA thrombus resolution may be achieved with the use of oral Factor Xa inhibitors, which in randomized trials were non-inferior to warfarin with regard to the incidence of the primary outcome measure (7), including any stroke or peripheral embolism in patients with non-valvular atrial fibrillation, but also ensure immediate and stable anticoagulation. Oral Factor Xa inhibitors have also demonstrated a better safety profile than warfarin.

2.2. TARGET PATHOLOGY DEFINITION

Non-valvular atrial fibrillation in patient with high atrial fibrillation-related thromboembolic risk, and LA or LAA thrombosis.

2.3. INFORMATION ON THE TEST PRODUCT

Edoxaban is an oral direct factor-Xa inhibitor similar to the previously developed molecules rivaroxaban and apixaban.

As reported in the approved SmPC, both animal and Phase I studies have demonstrated that edoxaban is highly effective in factor Xa-inhibition activity and reducing clot formation. In rat and monkey models, edoxaban demonstrated almost complete inhibition of factor-Xa activity and (in particular in monkeys) a rapid onset of inhibitory effect.

Edoxaban quickly reaches peak plasma concentrations in 1.5 hours; its half-life is between 10 and 14 hours. Oral bioavailability is quite high (more than 62%) and factor-Xa inhibition is highly selective, competitive, and concentration-dependent. Plasma concentrations of edoxaban are also closely correlated with the suppression of other coagulation indices and various platelet-activation parameters.

The results for all-cause mortality in the pivotal study ENGAGE AF-TIMI 48 study were 769 (3.99% per year) for subjects taking edoxaban 60 mg as opposed to 836 (4.35% per year) for warfarin [HR (95% CI): 0.91 (0.83 - 1.01)].

In the same study there was a significantly lower rate in favour of the edoxaban 60 mg treatment group compared with the warfarin group of major bleeding (2.75%, and 3.43% per year, respectively) [HR (95% CI): 0.80 (0.71, - 0.91); $p = 0.0009$], and intracranial hemorrhage (0.39%, and 0.85% per year, respectively) [HR (95% CI): 0.47 (0.34 - 0.63); $p < 0.0001$].

The lower rates of fatal bleeds were also significant for the edoxaban 60 mg treatment group compared with the warfarin group (0.21%, and 0.38%) [HR (95 % CI): 0. 55 (0.36 - 0.84); $p =$

0.0059 for superiority], primarily because of the reduction in fatal Intracranial haemorrhage bleeds [HR (95% CI): 0.58 (0.35 - 0.95); p = 0.0312].

2.4. STUDY RATIONALE

The aim of this open-label pilot study is to investigate the extent of LA/LAA thrombus resolution with edoxaban therapy in patients with non-valvular atrial fibrillation.

A subordinated aim of this study is the planning and design of a larger study directly comparing edoxaban vs warfarin in the same patient population. With the exception of few case reports, there are no data in the same patient population referred to antithrombotic treatments other than vitamin K antagonists.

As the main goal of this exploratory study is the estimation of the magnitude of the LA/LAA thrombus resolution with edoxaban, no control group with vitamin K antagonists has been considered, providing that, for the purpose of this study, the magnitude of the response of warfarin is satisfactory defined (1).

2.5. OVERALL RISK AND BENEFIT ASSESSMENT

Anticoagulant therapy is anyway necessary for the population under study

Patients with AF have an increased risk of recurrent embolism, and therefore should receive anticoagulant therapy. In particular, for patients with CHA₂DS₂-VASc score >1 the Guidelines for the management of atrial fibrillation (1) recommend an anticoagulant therapy in any case. Either oral anticoagulant therapy (OAC), including non-vitamin K oral anticoagulants (NOACs), or aspirin 75–325 mg daily are recommended, with preference of OAC to aspirin.

No use of placebo

Placebo is not used in this study, neither as a comparative agent nor as an add-on agent, in the cohort of patients under study.

Edoxaban is safer than warfarin

In the pivotal ENGAGE AF-TIMI 48 study (7) it has been demonstrated that more than half of the lower rates of all-cause deaths with edoxaban as compared to warfarin were directly attributable to fewer fatal bleeding events and non-fatal major bleeding that contributed to a death within 30 days. There were no differences between edoxaban and warfarin in deaths due to non-cardiovascular causes, nor for any of the 3 most common cardiovascular causes of death, sudden cardiac death, heart failure, ischemic stroke. However, warfarin was associated with approximately twice the risk of fatal bleeding as compared to edoxaban

Positive results with other NOACs

There have been few recent case reports about the resolution of LAA thrombus in patients treated with NOACs (6, 8-10), showing disappearance of thrombi after very 5 weeks or less of NOACs treatment, and consistently suggesting that such therapy might be effective the this clinical condition.

Summary of risk and benefit assessment

Taking into account all medical needs, the positive safety data of edoxaban compared to warfarin, and the encouraging efficacy data from drugs belonging to the same class, it can be reasonably concluded that the participation to this study does not expose the patient to unforeseen risks.

3. STUDY OBJECTIVES

3.1. PRIMARY OBJECTIVE

The primary objective of the study will be the definition of the extent of patients who, after 4 weeks of edoxaban treatment, will experience complete thrombus resolution by TEE.

3.2. SECONDARY OBJECTIVE(S)

Secondary objectives will be the assessment of bleeding events after 4 weeks of treatment with edoxaban and, after the same period, the incidence of any stroke or peripheral embolism and the time, when applicable, to electrical cardioversion.

4. ETHICAL CONSIDERATIONS RELATING TO THE STUDY

The trial will be conducted according to Good Clinical Practices (CPMP/ICH/135/95), as well as the Declaration of Helsinki and its subsequent amendments (see Appendix) and national regulations. This protocol and related documents (included the informed consent form) will be submitted for approval to independent local Ethics Committees before the study set up, according to national regulations.

All the protocol amendments or critical events liable to increase the risks incurred by the subjects or to compromise the validity of the study or subjects' rights will be submitted to the Coordinator, the concerned Authorities and the Ethics Committees.

After being informed orally and in writing of all aspects and constraints of the trial, as well as of their freedom to withdraw their participation at any time, patients will sign a consent form. A time for informed reflection on the protocol will be given to each patient before they give written consent and before starting the study procedures.

Patients will be made aware of their rights to decline to participate or to withdraw from the study at any time.

This study does not involve the use of placebo.

5. STUDY DESIGN

5.1. OVERALL DESCRIPTION

This is a pilot, non-controlled, open-label, 4-weeks study.

5.2. DISCUSSION OF THE STUDY DESIGN

5.2.1. Choice of the Study Population

A total of 25 patients with non-valvular atrial fibrillation, high atrial fibrillation-related stroke risk, and documented LA or LAA thrombosis will be included in the study.

5.2.2. Choice of the Study Design

With the exception of some case reports (6, 15), there are no studies conducted with NOACs to assess their efficacy in the resolution of non-valvular atrial thrombi once they are formed in the atria. For this reason, this study was designed to get preliminary clinical indications in order to plan a larger study directly comparing edoxaban and warfarin in the same patient population.

Due to its exploratory objective, no control group will be considered. Duration of the study is consistent with recommendations given by the guidelines, and with the reported clinical experiences (1, 6, 8-10, 15).

5.2.3. Choice of the Sample Size and the number of centres

There are no previous studies conducted with edoxaban on atrial thrombus dissolution, and this is a pilot trial. For this reason, sample size has been determined empirically, on the basis of case reports with similar products in this clinical conditions (6, 8-10, 15) and better described in section 14.

The involvement of 6-8 sites implies an enrolment of an average of about 4 patient per site to be recruited in about 15 months.

5.3. STUDY PERIOD

The planned start of enrolment is November 2017. The total duration of the enrolment phase is supposed to be 15 months and therefore the completion of the recruitment is expected by February 2019.

The last patient visit is expected by September 2018.

6. STUDY POPULATION

In this pilot study a total of 25 patients with non-valvular atrial fibrillation, high atrial fibrillation-related stroke risk and LA or LAA thrombosis will be recruited.

6.1. INCLUSION CRITERIA

Patients with all the following criteria will be eligible for inclusion in the study protocol:

1. Signed written informed consent
2. Males and females \geq 18 years of age
3. Female subjects must be postmenopausal (for at least 2 years), surgically sterile, abstinent, or, if sexually active, be practicing an effective method of birth control (e.g., prescription oral contraceptives, contraceptive injections, intrauterine device, double-barrier method, contraceptive patch, male partner sterilization) before entry and throughout the study; and, for those of childbearing potential, have a negative serum β -hCG pregnancy test at screening
4. Atrial fibrillation (AF) must be documented by ECG evidence (e.g., 12-lead ECG, rhythm strip, Holter, pacemaker interrogation) within 30 days before enrolment.
5. Subjects with newly diagnosed atrial fibrillation are eligible provided that:
 - a. there is evidence that the atrial fibrillation is non-valvular
 - b. there is ECG evidence on 2 occasions 24 hours apart, demonstrating atrial fibrillation
6. LA or LAA thrombosis documented by transesophageal echocardiography (TEE)

7. CHA₂DS₂-VASc score >1.

6.2. EXCLUSION CRITERIA

Patients with all the following criteria will not be eligible for inclusion in the study protocol:

Cardiac-related conditions

1. Hemodynamically significant mitral valve stenosis
2. Mechanical or biological prosthetic heart valve (annuloplasty with or without prosthetic ring, commissurotomy and/or valvuloplasty are permitted)
3. Transient atrial fibrillation caused by a reversible disorder (e.g., thyrotoxicosis, pulmonary embolism, recent surgery or myocardial infarction)
4. Known presence of atrial myxoma
5. Left ventricular thrombus
6. Active endocarditis.

Bleeding risk-related criteria

7. Active internal bleeding.
8. History of condition associated with increased bleeding risk including, but not limited to:
 - a. major surgical procedure or trauma within 30 days
 - b. clinically significant gastrointestinal bleeding within 6 months
 - c. previous intracranial, intraocular, spinal, atraumatic intra-articular bleeding
 - d. chronic hemorrhagic disorders
 - e. Any neoplasm, including intracranial neoplasm
 - f. Arterio-venous malformation or aneurysm.
9. Platelet count <90,000/ μ L at the screening visit
10. Sustained uncontrolled hypertension: SBP \geq 180 mmHg or DBP \geq 100 mmHg
11. Severe, disabling stroke (modified Rankin score of 4 to 5, inclusive within 3 months or any stroke < 14 days)
12. Transient ischemic attack within 3 days.

Concomitant or intercurrent therapies

13. Any oral anticoagulant therapy at the time of the baseline visit
14. Treatment with:
 - a. aspirin >160 mg daily
 - b. aspirin plus a thienopyridine within 5 days
 - c. intravenous antiplatelets within 5 days
 - d. fibrinolytics within 10 days.
15. Anticipated need for therapy with a non-steroidal anti-inflammatory drug in the next 4 weeks
16. Treatment with a strong inducer of cytochrome P450 and P glycoprotein, such as ketoconazole, itraconazole, voriconazole, posaconazole, ritonavir, lopinavir, telaprevir, indinavir, convartan, claritromycin or planned treatment during the study
17. Other indications for anticoagulant therapy
18. Hypersensitivity or intolerance to the study drug, including excipients.

Other concomitant or intercurrent conditions

19. Women of childbearing potential who do not want to adopt a contraceptive method during the study period and the following 4 weeks
20. Breast-feeding women during the study period and the following 4 weeks
21. Anemia (hemoglobin <10 g/dL) at the screening visit
22. Known significant liver disease (e.g., acute clinical hepatitis, chronic active hepatitis, cirrhosis), or ALT or AST >2 x ULN or total bilirubin >1.5 x ULN
23. Patients with moderate or severe renal impairment (CrCL <50 mL/min) or patients with end stage renal disease (CrCL < 15 mL/min) or on dialysis.

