6.3. WITHDRAWAL AND /EARLY DISCONTINUATION CRITERIA

In addition to screening failure, the reasons for a patient's premature withdrawal or early discontinuation from the study may be the following:

- The patient's or legal representative's decision that can occur for any reason and at any time

- The Investigator's decision in the patient's interest. Particularly, if a serious adverse event occurs and is considered by the Investigator liable to threaten the health of the patient
- An erroneous inclusion according to the protocol. The decision to maintain the patient or not in the study will be taken jointly by the Investigator and the Promoter
- Promoter's or Competent Authorities' motivated decision
- Other reasons, to be specified, such as: death, adverse events, lack of efficacy, major protocol violation, non-compliance, pregnancy, loss at follow-up.

The Investigator should attempt to collect, as soon as possible, the following information for a final assessment:

- reason(s) for withdrawal to be reported in the case report form
- evaluation of the patient's clinical condition
- if necessary, take appropriate therapeutic measures: management of an adverse effect or concomitant disease, prescription of another treatment
- recover the investigational product previously given to the patient.

In all cases, available data will be kept for the safety analysis.

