7. STUDY TREATMENT

All patients will receive edoxaban 60 mg once a day, with an open-label design, for 4 weeks. Edoxaban daily dose will be reduced to 30 mg/day in case of: body weight \leq 60 kg, or concomitant therapy with verapamil/quinidine/dronedarone.

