8. CONCOMITANT TREATMENTS

Any existing concomitant treatment, any new concomitant treatment or change in the dosage of an existing concomitant treatment during the course of the study must be noted on the CRF.

For all concomitant treatments taken during the study, the following information must be noted in the relevant section(s) of the CRF:

- The name of the treatment and its form
- The reason for prescription
- The route of administration
- The daily dose
- The duration.

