10.1. BASELINE VISIT

A screening assessment can occur on the same day of the baseline visit or up to 7 days before it. The patient will be assessed for the following:

- Collection of the signed informed consent
- Verification of inclusion/exclusion criteria
- Collection of demographic data, including: date of birth (month and year), gender, weight, height (calculated BMI), and race
- Medical history (with evaluation of CHA₂DS₂-VAS_C score and HAS-BLED scores)
- Information regarding AF
- Blood pressure, heart rate
- ECG
- Transthoracic echocardiogram (TTE)
- Transesophageal echocardiogram (TEE)
- Therapy: antithrombotic treatment and concomitant treatments (antihypertensives, heart failure and antiarrhythmic therapies, metabolic and anti-inflammatory, antithrombotic therapies for indications other than AF), and other selected drugs.
- Complete blood count; assessment of liver and renal function.

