15.1. PROTOCOL AMENDMENT

Neither the Investigator nor the Sponsor may alter the protocol without the authorization of the other party. All changes to the protocol are subject to an amendment, which must be dated and signed by both parties and must appear as an amendment to the protocol.

Substantial amendments are submitted for approval / authorisation to the Ethics Committees and Competent Authorities.

Urgent amendments are submitted for approval / authorisation to the Ethics Committees and Competent Authorities, but could be implemented immediately under specific conditions defined with the Sponsor.

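### Exclusion 16 names strong inducers as the excluded class, but its examples are ordinarily classed as strong inhibitors, so its wording does not bar an unlisted strong inhibitor

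*Protocol*

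**What the plan says.** Protocol section 6.2, item 16, under concomitant therapies, opens with "Treatment with a strong inducer of cytochrome P450 and P glycoprotein, such as ketoconazole, itraconazole", continues through other azoles and protease inhibitors, and closes with "telaprevir, indinavir, convartan, claritromycin or planned treatment during the study". The synopsis carries the same item with the same class word and ends "telaprevir, indinavir, conivaptan, claritromycin or planned treatment during the study". Neither copy corrects the other.

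The only other rule on interacting drugs is the dose rule in section 7, repeated in the synopsis. The dose falls from 60 mg to 30 mg/day for body weight of 60 kg or less, or for "concomitant therapy with verapamil/quinidine/dronedarone".

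Two further sections deal with other medicines, and both only collect information. Section 10.1 takes down therapy at baseline, including "antithrombotic therapies for indications other than AF), and other selected drugs". Section 8 says that existing, new or changed treatment "during the course of the study must be noted on the CRF".

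**The concern.** An exclusion criterion with an open list works through its class word: the examples illustrate the class, and the class word decides every drug that is not named. Here the two point in opposite directions. An inhibitor of these pathways would be expected to raise edoxaban exposure and an inducer to lower it. Section 2.3 of the protocol describes factor-Xa inhibition as concentration-dependent, so the direction matters.

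What is at stake is first a safety question. A patient taking a strong inhibitor that is not among the examples is not caught by the words of item 16. Unless that patient weighs 60 kg or less or takes one of the three dose-rule drugs, the dose would be 60 mg. Bleeding is a safety criterion of this trial (sections 9.2 and 14.8).

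**Working it through.** **The plan's own figure.** The only design figure is the two-sided 95% interval for 60% resolution in 25 patients (section 14.2).

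- Events: 0.60 × 25 = 15.
- Exact (Clopper-Pearson) lower limit: 2.5% quantile of Beta(15, 11) = 0.387.
- Exact upper limit: 97.5% quantile of Beta(16, 10) = 0.789.
- Result: 38.7% to 78.9%, which rounds to the stated 39-79%.

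The figure reproduces. Its inputs are a proportion and a sample size, so nothing in item 16 enters it and correcting the item leaves it as it is.

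The rest is a comparison of texts.

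**Step 1: the examples.** Item 16 names ketoconazole, itraconazole, voriconazole, posaconazole, ritonavir, lopinavir, telaprevir, indinavir, conivaptan and clarithromycin, 10 in all. (The body and synopsis spell conivaptan differently; I take it as one drug.) Assumption: all ten are ordinarily classed as strong inhibitors. Ritonavir has some inducing action too, but is ordinarily listed as a strong inhibitor. No typical inducer is named.

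**Step 2: what was probably meant.** The dose rule names 3 drugs, and its overlap with the 10 is 0. Halving the dose from 60 to 30 mg makes sense if the worry is too much edoxaban, not too little. The neighbouring drug exclusions, items 13 to 15, concern anticoagulants, antiplatelets, fibrinolytics and anti-inflammatories, which are also bleeding concerns. 'Inhibitor' is therefore the likely intent, but the protocol never says so.

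**Step 3: how item 16 can be read.**

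| Reading of item 16 | Ten named drugs | Unlisted strong inhibitor | Strong inducer |
|---|---|---|---|
| By its class word | excluded | not barred | excluded |
| By its examples | excluded | excluded | not barred |
| Cautiously, by both | excluded | excluded | excluded |

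The rows differ only for drugs that are not named.

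**Step 4: does another rule settle it at screening?**

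- Section 7 adjusts the dose for three named drugs and says nothing about other inhibitors.
- Sections 8 and 10.1 record therapy without barring any of it. Section 10.2 asks again at week 4, when the 28 days of treatment are over.
- Section 6.3 allows review of "An erroneous inclusion according to the protocol". On the literal wording, enrolling a patient on an unlisted inhibitor is not erroneous, so this route does not reach that patient.
- Section 6.3 also lets the investigator withdraw a patient in the patient's interest. That depends on judgement and does not say who is eligible.
- Section 2.3 cites the approved product information for product data. No section makes it govern eligibility.

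None of these closes the gap.

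**The case against.** The strongest reply is that no competent site would be misled. Ten examples point one way, the dose rule points the same way, and an investigator who knows these drugs will see the slip. A careful site would apply both the word and the examples and admit neither class. Other lines in section 6.2 also need a sensible reading: taken literally, its opening sentence would require a patient to meet every item before being excluded. Therapy is collected at baseline, and the investigator can withdraw a patient.

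Much of this stands. It makes harm less likely and keeps the point minor. It does not make the text correct, because the reply depends on sites replacing the class word with its opposite or adding a class that the text does not name. With 6-8 sites, the rule should not depend on that.

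It is also fair to say that the mismatch cannot be shown from the protocol alone, since no section classifies the drugs. The point rests on general pharmacology, and that is stated as an assumption.

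A reader might infer that both classes are admitted, or that the criterion fails altogether. The documents do not support that: no single reading in the table admits both classes, and the ten named drugs are out on every reading. A reader might also infer that the primary result is biased. Each patient is 1/25 = 4 percentage points of it, but nothing in the protocol indicates that any patient on such a drug would be enrolled.

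**Conclusion.** Item 16 is wrong as written, in both places, and the error is minor. The class word is contradicted by every example that follows it, 'inhibitor' was probably meant, and on the literal wording a patient taking an unlisted strong inhibitor is not barred and could receive 60 mg. No other section resolves this at screening.

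Its size cannot be put in patients: the number affected is unknown and may be 0. The sample size, the 39-79% interval and the planned analyses do not change. The possible consequence is excess bleeding risk in an individual patient, not a distorted estimate that can be calculated.

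The conclusion assumes the ordinary classification of the ten drugs and takes the list as open, as its wording indicates. It does not assume that the sponsor meant to exclude inducers. A reader might infer that from the class word, but no example supports it.

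**What to change.** In item 16 of section 6.2 and in item 16 of the synopsis, replace 'inducer' with 'inhibitor' and keep the listed drugs as they are. That corrects the defect.

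The sponsor should decide separately whether strong inducers are also to be excluded, since they could lower exposure and with it thrombus resolution, the primary endpoint. If so, add a clause of its own for them, so that one class word does not have to serve both.

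The cost is one word in two places, made by a dated and signed amendment under section 15.1. Because it changes which drug class the text excludes, it may count as substantial, and "Substantial amendments are submitted for approval / authorisation to the Ethics Committees and Competent Authorities". Design, sample size and analysis stay as they are.
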